8.2.5. Vital Signs Analyses

Vital signs are assessed in this study according to the schedule outlined in the Time and Events table (see Section 10.2.1) and include the following assessments:

- Height
- HR
- Weight
- Estimated Dry Weight

Summaries and analyses of BP values are described in earlier safety sections and will not be included with vital signs summaries. However, BP values will be included in PCI summaries.

CONFIDENTIAL

201410

The vital signs analyses will be based on the Safety population, unless otherwise specified.

8.2.5.1. Overview of Planned Vital Signs Analyses

Table 13 provides an overview of the planned vital signs analyses.

Table 13 Overview of Planned Vital Signs Analyses

Parameter	Absolute				Change from Baseline			
	Summary		Individual		Summary		Individual	
	T	F	F	L	T	F	F	L
Vital Signs								
Vital Signs by Visit	Y				Y			
Summary of Worst Case Vital Signs Results by PCI Criteria	Y							
All Vital Signs for Subjects with Any Value of Potential Clinical Importance				Y				

NOTES :

- T = Table, F = Figure, L = Listing, Y = Yes display generated.
- Summary = Represents TFL related to any summaries (i.e. descriptive statistics) of the observed raw data.
- Individual = Represents FL related to any displays of individual subject observed raw data.

8.2.5.2. Planned Vital Signs Display Details

Vital sign values will be summarized using mean, standard deviation, minimum, P25, median, P75, and maximum for each scheduled visit and for baseline and end of treatment by treatment group.

Vital sign change from baseline values will be summarized using mean, standard deviation, minimum, P25, median, P75, and maximum for each scheduled visit and for end of treatment by treatment group.

The number and percentage of subjects with on-treatment or post-treatment worst case vital sign results relative to PCI criteria (see Section 10.8.1) which are post-baseline relative to baseline will be summarized by test, category and treatment group. See Section 10.6.4 for additional information on worst case values and PCI categories. Pre-dialysis BP values outside of the PCI range will be summarized separately.

The difference between on-treatment post-dialysis weight and estimated dry weight will be summarized using mean, standard deviation, minimum, P25, median, P75, and maximum for each scheduled visit during the evaluation period and for baseline and end of treatment by treatment group. A corresponding line plot will be provided to display this data graphically.

A listing of all vital signs data for subjects with on-treatment vital signs values outside of PCI criteria will be provided.

8.2.6. Electrocardiograms

Electrocardiograms (ECGs) will be read locally and ECG data will not be included in summary tables or individual subject listings.

8.2.7. Pregnancies

A listing of all subjects who became pregnant during the study will be included.

8.2.8. Other Safety Analyses

Medical Conditions

A listing of all medical conditions for all subjects will be provided by treatment group. Each subject's corresponding medical condition(s) will be provided using the medical history free text.

COVID-19 Analyses

The following COVID-19 related displays will be provided.

A summary of the number and percentage of subjects for the following assessments will be produced: Case Diagnosis, COVID-19 Test performed, and Results of the COVID-19 test.

A summary of exposure adjusted incidence rates over time (see Section 10.6.4) will be produced by treatment group for any treatment emergent AE, any treatment emergent SAE, and any treatment emergent Severe AE, for two periods – pre COVID-19 pandemic and during COVID-19 pandemic. The summary will be produced overall, by Country, Region, Sex, and by Age at randomization (Grouping 2) (see Section 10.10.1). A summary of exposure adjusted incidence rates by treatment group will also be produced for Common (>5%) AEs for two periods – pre COVID-19 pandemic and during COVID-19 pandemic.

8.3. Pharmacokinetic Analyses

8.3.1. Overview of Planned Pharmacokinetic Analyses

The pharmacokinetic (PK) analyses will be based on the “Pharmacokinetic” population, unless otherwise specified.

[Table 14](#) provides an overview of the planned analyses.

CONFIDENTIAL

201410

Table 14 Overview of Planned Pharmacokinetic Analyses for GSK1278863, and/or GSK2391220 (M2), GSK2506104 (M3) and GSK2531401 (M13)

Parameter	Untransformed							Log-Transformed						
	Stats Analysis			Summary		Individual		Stats Analysis			Summary		Individual	
	T	F	L	T	F	F	L	T	F	L	T	F	F	L
GSK1278863, GSK2391220 (M2), GSK2506104 (M3) and GSK2531401 (M13)														
GSK1278863 and Metabolites Plasma Pharmacokinetic Concentration Time Data (ng/mL) by Treatment				Y	Y ¹	Y	Y						Y ¹	Y
GSK1278863 and Metabolites Plasma Pharmacokinetic Parameter ² Data				Y			Y					Y		
GSK1278863														
GSK1278863 Dose Parameter Data				Y			Y							
GSK1278863 Special Parameter ³ Data				Y			Y				Y			

NOTES :

- T = Table, F = Figure, L = Listings, Y = Display generated.
- Stats Analysis = Represents TFL related to any formal statistical analyses (i.e. modelling) conducted.
- Summary = Represents TFL related to any summaries (i.e. descriptive statistics) of the observed raw data.
- Individual = Represents FL related to any displays of individual subject observed raw data.

1. Mean and median plots will be generated
2. C_{max}, T_{max}, C_{tau}
3. C_{tau}/1mg Dose, C_{tau}/avg Dose EP TIR, C_{tau}/avg Dose EP, C_{tau}/ Dose at MACE, C_{tau}/ Final Dose for subjects without MACE, C_{tau}/ Dose at MACE++, C_{tau}/ Final Dose for subjects without MACE++, C_{max}/1mg Dose, C_{max}/avg Dose EP TIR, C_{max}/avg Dose EP, C_{max}/ Dose at MACE, C_{max}/ Final Dose for subjects without MACE, C_{max}/ Dose at MACE++, C_{max}/ Final Dose for subjects without MACE++

8.3.2. Drug Concentration Measures

Refer to [Appendix 5: Data Display Standards & Handling Conventions \(Section 10.5.3 Reporting Process & Standards\)](#).

8.3.3. Pharmacokinetic Parameters**8.3.3.1. Deriving Pharmacokinetic Parameters**

- Refer to [Appendix 5: Data Display Standards & Handling Conventions \(Section 10.5.3 Reporting Process & Standards\)](#).
- The pharmacokinetic parameters of parent GSK1278863, and metabolites (GSK2391220 (M2), GSK2506104 (M3), and GSK2531401 (M13)) will be calculated by programming methods.

CONFIDENTIAL

201410

- All calculations of non-compartmental parameters will be based on actual sampling times.
- Pharmacokinetic parameters described in [Table 15](#) will be determined from the plasma concentration-time data, as data permits.

Table 15 Derived Pharmacokinetic Parameters for GSK1278863, and/or GSK2391220 (M2), GSK2506104 (M3) and GSK2531401 (M13)

Parameter	Parameter Description
GSK1278863, GSK2391220 (M2), GSK2506104 (M3) and GSK2531401 (M13)	
Tmax	Time to reach Cmax, determined directly from the concentration-time data.
Ctau	Observed concentration at dosing interval (tau=24 h, predose sample)
Cmax	Maximum observed concentration, determined directly from the concentration-time data.
GSK1278863	
Avg Dose during EP TIR	The average daily GSK1278863 dose when the subject is on-treatment and in target Hgb range during the evaluation period (EP) Weeks 28-52 (see Section 10.6.3.1). Evaluable Hgb values are used to determine time in range. Subjects who permanently stop randomized treatment before the beginning of the EP, and subjects who have 0% time in range (e.g., subjects who have an evaluable Hgb below or above range for the entire EP) will have a missing value for this parameter.
Avg Dose EP	The average daily GSK1278863 dose when the subject is on-treatment during the EP.
Dose at first MACE	The daily GSK1278863 dose at the time of the subject's first on-treatment adjudicated MACE. If the subject does not have an on-treatment adjudicated MACE, this value is missing.
Final Dose for Subjects without MACE	For subjects without an on-treatment adjudicated MACE, this is the subject's final GSK1278863 dose during the study.
Dose at first MACE++	The daily GSK1278863 dose at the time of the subject's first on-treatment adjudicated MACE++ (defined as the first adjudicated MACE, hospitalization for heart failure, or thromboembolic event) If the subject does not have an on-treatment adjudicated MACE++, this value is missing.
Final Dose for Subjects without MACE++	For subjects without an on-treatment adjudicated MACE++, this is the subject's final GSK1278863 dose during the study.
Ctau/1mg Dose	Ctau extrapolated to 1mg dose: Observed Ctau divided by dose administered on the PK day
Ctau/Avg Dose EP TIR	Ctau extrapolated to average dose during EP TIR: Ctau/1mg multiplied by the average daily GSK1278863 dose when the subject is on-treatment and in target Hgb range during Weeks 28-52 (see Section 10.6.3.1). Evaluable Hgb values are used to determine time in range.
Ctau/Avg Dose EP	Ctau extrapolated to average dose during EP: Ctau/1mg multiplied by the average daily GSK1278863 dose during the EP.

CONFIDENTIAL

201410

Parameter	Parameter Description
Ctau/Dose at first MACE	Ctau extrapolated to dose at first on-treatment adjudicated MACE: Ctau/1mg multiplied by the daily GSK1278863 dose at the time of the subject's first on-treatment adjudicated MACE.
Ctau/Final Dose for subjects without MACE	For subjects without an on-treatment adjudicated MACE, this is the subject's Ctau/1mg multiplied by the subject's final daily GSK1278863 dose during the study.
Ctau/Dose at first MACE++	Ctau extrapolated to dose at first on-treatment adjudicated MACE++: Ctau/1mg multiplied by the daily GSK1278863 dose at the time of the subject's first on-treatment adjudicated MACE++.
Ctau/Final Dose for subjects without MACE++	For subjects without an on-treatment adjudicated MACE++, this is the subject's Ctau/1mg multiplied by the subject's final daily GSK1278863 dose during the study.
Cmax/1mg Dose	Cmax extrapolated to 1mg dose: Observed Cmax divided by dose administered on the PK day
Cmax/Avg Dose EP TIR	Cmax extrapolated to average dose during EP TIR: Cmax/1mg multiplied by the average daily GSK1278863 dose when the subject is on-treatment and in target Hgb range during Weeks 28-52 (see Section 10.6.3.1). Evaluable Hgb values are used to determine time in range.
Cmax/Avg Dose EP	Cmax extrapolated to average dose during EP: Cmax/1mg multiplied by the average daily GSK1278863 dose during the EP.
Cmax/Dose at first MACE	Cmax extrapolated to dose at MACE: Cmax/1mg multiplied by the daily GSK1278863 dose at the time of the subject's first on-treatment adjudicated MACE.
Cmax/Final Dose for subjects without MACE	For subjects without an on-treatment adjudicated MACE, this is the subject's Cmax/1mg multiplied by the subject's final daily GSK1278863 dose during the study.
Cmax/Dose at first MACE++	Cmax extrapolated to dose at MACE++: Cmax/1mg multiplied by the daily GSK1278863 dose at the time of the subject's first on-treatment adjudicated MACE++.
Cmax/Final Dose for subjects without MACE++	For subjects without an on-treatment adjudicated MACE++, this is the subject's Cmax/1mg multiplied by the subject's final daily GSK1278863 dose during the study.

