9.4.6. Pharmacokinetic/Pharmacodynamic Analyses

The 'PK Population' is defined as subjects for whom a PK sample was obtained and analyzed. This will be the population used for all the PK displays.

The following plasma PK parameters will be determined for daprodustat and metabolites: C_{τ} (pre-dose) and C_{\max} .

Plasma daprodustat and metabolites concentration data will be listed and summarized by planned collection time and daprodustat dose administered at PK visit. PK parameter data will be listed and summarized by daprodustat dose administered at PK visit, and dose-normalized (per mg) PK parameter data will be summarized.

All PK data will be stored in the Archives, GlaxoSmithKline Pharmaceuticals, R&D.

The following exploratory graphics will be created. Based on these, and the efficacy and safety results from other Phase 3 studies, post-hoc exploratory exposure-response/safety modelling may be conducted, including exploratory graphics with metabolites. Further details will be provided in the RAP.

- Scatter plots of daprodustat PK parameters (C_{τ} and C_{\max}) dose normalized to 1 mg vs. percent time in range during EP.
- Scatter plots of average daprodustat dose during EP vs. percent time in range during EP.
- Scatter plots of daprodustat PK parameters (C_{τ} and C_{\max}) dose normalized to average dose during EP vs. percent time in range during EP.
- Scatter plots of daprodustat PK parameters (C_{τ} and C_{\max}) dose normalized to 1 mg vs. change from baseline of Hgb during EP.
- Scatter plots of average daprodustat dose during EP vs. change from baseline of Hgb during EP.
- Scatter plots of daprodustat PK parameters (C_{τ} and C_{\max}) dose normalized to average dose during EP vs. change from baseline of Hgb during EP.
- Boxplots of daprodustat PK parameters dose normalized to 1 mg by subjects with or without MACE or a combined safety endpoint of MACE + thromboembolic event + hospitalization for heart failure

- Boxplots of daprodustat PK parameters dose normalized to dose at time of MACE or combined safety endpoint (or end of treatment if no endpoint) by subjects with or without MACE or combined safety endpoint

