8.4. Pharmacokinetic / Pharmacodynamic Analyses

- The primary goal of this analysis is to characterize the pharmacokinetic/pharmacodynamic relationship of parent GSK1278863 and efficacy and safety endpoints in the “Pharmacokinetic” population from this study.
 - The influence of subject demographics and baseline characteristics, including disease activity in this population may be investigated.

CONFIDENTIAL

201410

- A summary of the planned population pharmacokinetic/pharmacodynamic analyses are outlined below:
 - Relationships between drug exposure and selected efficacy, MACE and MACE ++ events will be explored and characterized as data permit. The exposure will be estimated on the sparse PK collected in a sub-set of the study population. The data may be dose- extrapolated to the dose administered during the PK collection period. Any changes to the proposed analyses would be described in the CSR.

Table 16 Overview of Planned Pharmacokinetic / Pharmacodynamic Analyses for GSK1278863

Parameter	Untransformed						Log-Transformed							
	Stats Analysis			Summary		Individual		Stats Analysis			Summary		Individual	
	T	F	L	T	F	F	L	T	F	L	T	F	F	L
GSK1278863														
Scatter plot of % Time Evaluable Hgb in Range during EP vs. Avg Dose EP TIR						Y								
Scatter plot of Evaluable Hgb Change from Baseline during EP vs. Avg Dose EP						Y								
Scatter plot of % Time Evaluable Hgb in Range during EP vs. Ctau/Avg Dose EP TIR						Y								
Scatter plot of Evaluable Hgb Change from Baseline during EP vs. Ctau/Avg Dose EP						Y								
Boxplot of Ctau/Dose at On-treatment MACE or MACE++ by Subjects with or without On-treatment MACE or MACE++						Y								
Scatter plot of % Time Evaluable Hgb in Range during EP vs. Cmax/Avg Dose EP TIR						Y								
Scatter plot of Evaluable Hgb Change from Baseline during EP vs. Cmax/Avg Dose EP						Y								
Boxplot of Cmax/Dose at On-treatment MACE or MACE++ by Subjects with or without On-treatment MACE or MACE++						Y								

NOTES :

- T = Table, F = Figure, L = Listings, Y = Display generated.
- Stats Analysis = Represents TFL related to any formal statistical analyses (i.e. modelling) conducted.
- Summary = Represents TFL related to any summaries (i.e. descriptive statistics) of the observed raw data.
- Individual = Represents FL related to any displays of individual subject observed raw data.

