10.4.1.2. Treatment States for CV Endpoint Data

Treatment State	Definition
Pre-Treatment	Date < Treatment Start Date
On-Treatment	Treatment Start Date ≤ Date ≤ Last Non-Zero Dose Date + 28 days
Post-Treatment	Date > Last Non-Zero Dose Date + 28 days
Post-Randomization	Randomization Date ≤ Date

NOTES:

- If the last non-zero dose date is missing and the treatment start date is non-missing and Date ≥ Treatment Start Date, then the assessment will be considered to be On-Treatment
- Treatment state definitions use the imputed CV endpoint date

10.4.1.3. Treatment States for BP, Lipid Parameters, Clinical Chemistry, Hematology, Other Laboratory Tests, Hepatobiliary (Liver) and Vital Signs Data

Treatment State	Definition
Pre-Treatment	Date ≤ Treatment Start Date
On-Treatment	Treatment Start Date < Date ≤ Last Non-Zero Dose Date + 1 day
Post-Treatment	Date > Last Non-Zero Dose Date + 1 day
Post-Randomization	Randomization Date < Date

NOTES:

- If the last non-zero dose date is missing and the treatment start date is non-missing and Date > treatment start date, then the assessment will be considered to be On-Treatment

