
Last Non-Zero Dose Date
 
 • Date of last actual dose of randomized study treatment from IP Discontinuation eCRF form. 
 ○ The dose steps used by the dosing algorithm described in the protocol include a dose hold or a zero dose. If subjects are assigned by the algorithm to a zero dose, they do not receive randomized treatment for that period. Hence, it would be possible for a subject to complete the study, while still following the dosing algorithm, but not actually be taking any actual randomized treatment. The last non-zero dose date, then captures the latest date in the study that a subject physically took a dose of randomized treatment. • The eCRF allows for the possibility of partial or missing dates to be recorded for the last actual dose of randomized study treatment on the IP Discontinuation form (i.e., missing day, or day and month, or day and month and year). In such a case, or in case of subjects who have a non-missing treatment start date, but are missing an IP Discontinuation form, the following conventions will be applied in order to impute a last non-zero dose date: 
 ○ Missing day: 
 ▪ The last day of the month will be used, unless the treatment stop date also occurs in the same month; in this case, the treatment stop date will be used. ○ Missing day and month; 
 ▪ ‘31’ will be used for the day and ‘Dec’ will be used for the month, unless the treatment stop date also occurs in the same year; in this case the treatment stop date will be used. ○ Missing day, month, and year: 
 ▪ Treatment stop date will be used only for subjects who have a non-missing treatment start date.

CONFIDENTIAL

201410

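### The exposure–MACE boxplots read dose at the event in cases and at the end of treatment in everyone else, with no zero-dose rule, so they mix exposure with time on titration

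*SAP*

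**What the plan says.** SAP 8.3.3.1 (Table 15) sets one reference dose for cases and another for the rest. Cases get "The daily GSK1278863 dose at the time of the subject's first on-treatment adjudicated MACE". The others follow a different rule: "For subjects without an on-treatment adjudicated MACE, this is the subject's final GSK1278863 dose during the study". Each dose is multiplied by the subject's own per-mg Ctau or Cmax; for event-free subjects, "this is the subject's Ctau/1mg multiplied by the subject's final daily GSK1278863 dose during the study". The same pair of rules is repeated for MACE++, which adds hospitalization for heart failure and thromboembolic events. SAP 8.4 (Table 16) then shows subjects with and without the event in one boxplot. Protocol 9.4.6 already had this design, with parameters "dose normalized to dose at time of MACE or combined safety endpoint (or end of treatment if no endpoint").

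Two other definitions bear on the dose at the event. SAP 10.4.1.2 counts a cardiovascular event as on-treatment when "Treatment Start Date ≤ Date ≤ Last Non-Zero Dose Date + 28 days". SAP 10.6.1 says: "The dose steps used by the dosing algorithm described in the protocol include a dose hold or a zero dose". Neither Table 15 nor Table 16 says what dose applies after stopping or during a hold. Table 14 marks a log-transformed summary for these extrapolated parameters.

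SAP 2.1 drops the MACE boxplots normalized to 1 mg, giving a reason that concerns efficacy displays. SAP 2.2 still lists them, but Table 16 does not.

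**The concern.** The two boxes are read on different clocks. A case is read at whatever point in titration the event occurs. An event-free subject is read at the end of treatment, after up to 52 weeks of adjustment. Protocol 4.4.1 expects individual dose changes in the first few months. The groups can therefore differ in plotted exposure when exposure has no effect on MACE, and a real relation can be masked or exaggerated.

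The zero-dose gap adds to this. Read literally, an event in the 28 days after the last dose, or during a hold for high Hgb, is plotted at zero exposure, and a zero cannot enter the log-transformed summary. An event-free subject who finishes on a hold has the same problem. The display that did not depend on when the dose was read has been removed, so nothing in Table 16 offsets the mismatch.

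**Working it through.** The documents give no figure for this display, so there is none to reproduce.

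**1. What drives the contrast.** Plotted value = (Ctau ÷ dose on the PK day) × reference dose, and likewise for Cmax. The first factor comes from one visit (Week 4, 8 or 12; Protocol 7.5). The choice of reference dose is therefore where the clocks diverge. The dose ladder is 1, 2, 4, 6, 8, 10, 12, 16, 24 mg (SAP 10.6.3.5), with starts of 1, 2 or 4 mg (Protocol Table 3).
- Rising: a subject goes 2→4→6→8 mg. An event at 2 mg is plotted at 2/8, a quarter of the value the same subject would have if event-free.
- Falling: a subject goes 4→2→1 mg. An event at 4 mg is plotted at 4/1, four times the event-free value.

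**2. How much of the event window is exposed to the problem.** Protocol 9.2.1 assumes up to about 30% stop treatment before Week 28. With a constant stopping hazard (assumption), h = −ln(0.70)/28 = 0.01274 per week.
- On-drug time to Week 52 = (1 − e^(−52h))/h = (1 − 0.516)/0.01274 = 38.0 weeks per subject.
- Adding the 28-day tail gives 38.0 + 4 = 42.0 weeks. The tail is 4/42.0 = 9.5% of the window. From premature stoppers alone it is 0.484 × 4/42.0 = 4.6%.
- On-drug time before Week 28 = 0.30/0.01274 = 23.6 weeks, or 56% of the window.

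**3. Null simulation.** There were 60,000 subjects per scenario, and exposure had no effect on MACE. The following assumptions are not in the documents: starts 25% at 4 mg, 50% at 2 mg, 25% at 1 mg; moves every 4 weeks; half of events fatal; event rate 0.4 per year; log-normal per-mg Ctau. A PK sample was required. Entries are the median exposure in cases divided by that in event-free subjects, with the Weeks 0–12 hazard multiplied by 1 / by 3. The true value is 1.

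| Assumed titration | Zero read literally | Last non-zero dose carried |
|---|---|---|
| Net up | 0.72 / 0.67 | 0.88 / 0.76 |
| Mild up | 0.79 / 0.78 | 0.91 / 0.85 |
| Symmetric steps | 0.83 / 0.84 | 0.93 / 0.94 |
| Net down | 0.91 / 0.98 | 1.00 / 1.03 |

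Under the literal reading, 8–16% of cases and 2–8% of event-free subjects had a zero dose.

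**4. Poor responders at higher risk.** If hyporesponse raises both dose and MACE risk, with exposure itself inert, the ratio is 0.92–0.99 with literal zeros and 1.04–1.13 with the last non-zero dose.

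**5. Same-time comparison.** Comparing each case with a subject at risk at the same study time, under one zero-dose rule, gives 0.95–1.04 in all 16 scenarios of step 3. In the hyporesponse scenarios it gives 1.13–1.18. It removes the clock artefact but not confounding by response.

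**The case against.** The strongest reply is that no direction of bias follows from the plan. Protocol 4.4.1 says starting doses were chosen so that subjects would reach target Hgb, and Protocol Appendix 3 has both increase and decrease rules. The size depends on an assumed eventual dose. In a separate simulation the ratio was 0.70–0.77 with the needed dose centred at 6–8 mg, but 0.94–0.96 when it was centred at 2 mg. This stands, and any figure must be given as conditional.

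Second, very early cases are partly screened out. A plotted point needs a PK sample, taken once at Week 4, 8 or 12 in in-center HD subjects, so a fatal event before sampling never appears. Restricting events to Week 12 onward, even with the 6–8 mg assumption, gives 0.82–0.92. This stands too: the documents do not show that cases are mostly early, and the 4-fold example is an extreme.

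Third, zero is one reading of an unwritten rule. The nearest SAP convention, for most recent dose before a visit (10.6.3.5), takes the final exposure record after a permanent stop. Event-free subjects can also stop early or end on a hold. The supportable statement is that the rule is missing for both groups.

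Fourth, the plots are exploratory, no testing is planned, and the rule is disclosed in the protocol. That limits the consequence but leaves the mismatch in place.

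**Conclusion.** The mismatch is a stated rule and holds. The boxplots compare different time points without a zero-dose convention, so a difference between the boxes cannot be read as exposure–response. If doses rise over time, cases would look less exposed with no true effect, by a ratio of about 0.7–0.9 under the assumptions shown. Under net down-titration with the last non-zero dose carried the ratio is 1.00–1.03, and with hyporesponse linked to risk it can exceed 1.

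A reader might infer that cases are bound to look under-exposed, so that the display hides harm. The documents do not support that, because they never state the direction of titration. Nor is this the only look the plan allows. It is the only planned display of exposure against MACE, but Protocol 9.4.6 permits later exposure–safety modelling, and SAP 8.4 says these relationships will be explored as data permit.

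The consequence is minor. Protocol 9.4.4.1 expects fewer than 80 first MACE in both arms, so fewer than 40 on daprodustat if split evenly (assumption), and fewer again with a PK sample. No test, error rate or primary result is affected. This is a cheap improvement to an exploratory safety graphic.

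**What to change.** Amend SAP Tables 15 and 16 as follows.

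1. Define the analysis dose at MACE or MACE++ as the last non-zero daily dose on or before the event date, using no dosing information from after the event. This keeps zeros out of the log-transformed summary, including for an event late in a long hold.
2. Replace the final-dose parameters for event-free subjects. For each case, take the dose under the same rule, on the same treatment day, in PK-population subjects who are then event-free and still within the same cardiovascular on-treatment window.
3. Flag points where the subject was on a hold or had stopped treatment on that date.

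Dosing and event dates are already held, so the cost is SAP wording and some extra programming. A comparator may appear in more than one risk set, which a footnote should say. The footnote should also say that same-time comparison does not remove confounding by poor response. Trial conduct is unaffected.
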